3.4 Duration of the study participation

The study duration consists of the following periods:

Screening Period: 28 days

Treatment Period: All patients will receive a continuous 28-day treatment cycle of ASLAN003 until disease relapse, treatment failure (defined as failure to achieve a PR or higher within 4 cycles) unacceptable toxicity, withdrawal of consent or death.

Follow-up Period: All patients will be required to complete a safety follow-up visit within 28 days after the last dose of study treatment. All patients achieving CR or CRi will be followed for survival every 12 weeks post end of treatment (EOT) until disease relapse or death (in the absence of disease relapse) to find out the RFS.

Visit Schedule: In order to address the primary objectives of the study, if treatment is interrupted for any reason, it is important that all planned safety and efficacy assessments are performed at the scheduled time, regardless of whether the patient is receiving study treatment, or not, at the time.

The planned duration of entire study (treatment and follow-up) is approximately 2 years.

4 STUDY POPULATION

The study population consists of AML patients who are ineligible for standard treatment including but not limited to the following conditions:

- Newly diagnosed patients who are ineligible for standard therapy namely standard dose induction chemotherapy and reduced dose chemotherapy;
- Patients who relapsed from prior remission;
- Patients who failed to respond to prior therapy including chemotherapy, hypomethylating agents, and bone marrow transplantation.

Patients must be able to provide written consent; meet all the inclusion criteria and none of the exclusion criteria, stated below.

4.1 Inclusion Criteria

Patients will be enrolled into the study only if they meet all of the following criteria:

1. Patients who are of or older than the legal age in the respective countries at the time when written informed consent is obtained
2. Patients who are able to understand and willing to sign the informed consent form (ICF)
3. Patients who are diagnosed with AML according to the 2016 revision to the World Health Organization classification of myeloid neoplasms and acute leukemia (refer to Appendix 1: WHO Classification of Acute Myeloid Leukemia)
4. Patients who have a sufficient archival or fresh BM aspiration sample for the evaluation of relevant exploratory endpoint.

Note: Patients who do not have sufficient archival BM aspiration sample and refuse to repeat the procedure may be enrolled in the trial only after written confirmation by ASLAN

5. Patients who are ineligible for standard treatment of AML including but not limited to the following conditions:
 - Newly diagnosed patients who are ineligible for standard therapy namely standard dose induction chemotherapy and reduced dose chemotherapy;
 - Patients who relapsed from prior remission;
 - Patients who failed to respond to prior therapy including chemotherapy, hypomethylating agents, and bone marrow transplantation.
6. Patients who have an Eastern Cooperative Oncology Group (ECOG) performance status of ≤ 2
7. Patients with adequate renal and hepatic function, as defined below:
 - Estimated Glomerular Filtration Rate (eGFR) or creatinine clearance (CrCl) (CrCL calculated by the Cockcroft and Gault method) ≥ 40 ml/min/1.73 m²
 - Total bilirubin, AST, and ALT $\leq 1.5 \times$ ULN

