4.2 Exclusion Criteria

Patients will not be enrolled in the study if they meet any of the following criteria:

1. Patients who are diagnosed with *de novo* myeloid sarcoma without bone marrow involvement

2. Patients who are diagnosed with acute promyelocytic leukemia/retinoic acid receptor alpha (*PML-RARA*)
3. Patients who received any other standard or investigational treatment for their leukemia within the last 7 days before starting the first dose of study drug, with the exception of leukapheresis and hydroxyurea
4. Patients with unresolved serious toxicity (\geq CTCAE 4.03 Grade 2) from prior administration of standard or investigational treatment for their leukemia
5. Patients who have a positive test for human immunodeficiency virus (HIV), viral hepatitis C infection (patients with sustained viral response are not excluded), active viral hepatitis B infection (positive hepatitis B surface antigen [HBsAg]) with hepatitis B virus DNA exceeding 2000 IU/ml
6. Patients who have a known history of liver cirrhosis Child-Pugh score B or C
7. Patients who have any history of other malignancy unless in remission for more than 1 year (skin carcinoma and carcinoma-in-situ of uterine cervix treated with curative intent is not exclusionary)
8. Female patients who are pregnant or breast-feeding
9. Patients with a known history of alcohol or drug addiction on the basis that there could be a higher risk of non-compliance to study treatment per Investigator's discretion
10. Patients with a history or presence of a clinically significant condition which in the opinion of the Investigator could jeopardize the safety of the patient or the validity of the study results
11. Patients who have been previously treated with ASLAN003

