6.2 Efficacy Variables

Efficacy will be evaluated with BM aspiration and peripheral blood results based on the IWG Criteria¹⁶ for AML (Cheson, 2003). For patients without sufficient archival BM sample, BM aspiration will be performed during Screening. All patients will receive bone marrow aspiration for efficacy assessment on Day 1 of Cycle 2, 3, 4, 5 and will be repeated every 12 weeks after Cycle 5. Patients who've already achieved CR could omit the bone marrow aspiration at subsequent visits if there is a normal complete blood count with differential of the peripheral blood. Investigator may perform more frequent exam if required based on clinical judgment. In order to address the primary objectives of the study, if treatment is interrupted for any reason, it is important that all planned safety and efficacy assessments are performed at the scheduled time, regardless of whether the patient is receiving study treatment, or not, at the time

BM aspiration smears will be processed locally.

Following treatment discontinuation, patients who have achieved a CR or CRi, will continue to be followed up for every 12 weeks to assess the relapse free survival. For patients who have not achieved a CR or CRi during treatment, no further follow-up is required following treatment discontinuation.

These criteria categorize the visit response into the following response classifications:

- CR with incomplete recovery of neutrophils and platelets (CRi):

Achievement of CRi requires patients to satisfy all of the following:

- A disappearance of blasts in the peripheral blood.
 - A decrease in BM blasts to <5% total BM nucleated cells demonstrated in BM aspirate.
 - Absence of Auer rods
 - No persistent extramedullary leukaemia
-
- Complete Remission:
Patient satisfies all of the criteria above and in addition has:
 - Recovery of Neutrophils to $\geq 1.0 \times 10^9/L$ and Platelets to $\geq 100 \times 10^9/L$
 - Transfusion-independence

 - Partial Remission:
A PR is defined as recovery of neutrophils to $\geq 1.0 \times 10^9/L$ and Platelets to $\geq 100 \times 10^9/L$ and either:

- If the pre-treatment bone marrow blast percentage was 50% to 100%, the percentage of blast must decrease to a value between 5% and 25%
 - If the pre-treatment BM blast percentage was 20% to less than 49%, they must decrease by at least half to a value of more than 5%
 - A reduction in BM blast cells to <5% but with persistence of Auer rods.
- **Treatment failure:**

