3.1.1 Overall Complete Remission Rate

Overall complete remission rate (OCRR) is a co-primary endpoint in Part 1 and the primary endpoint in Part 2. It will be derived programmatically from the BM aspiration and peripheral blood results based on the IWG Criteria¹⁶ for AML (Cheson, 2003) as described below.

For patients without sufficient archival BM sample, BM aspiration will be performed during Screening. All patients will receive bone marrow aspiration for efficacy assessment on Day 1 of Cycle 2, 3, 4, 5 and will be repeated every 3 cycles after Cycle 5. Patients who've already achieved CR could omit the bone marrow aspiration at subsequent visits if there is a normal complete blood count with differential of the peripheral blood. Investigator may perform more frequent exam if required based on clinical judgment.

BM aspiration smears will be processed locally.

Following treatment discontinuation, patients who have achieved a CR or CRi, will continue to be followed up for every 12 weeks to assess the relapse free survival. For patients who have not achieved a CR or CRi during treatment, no further follow-up is required following treatment discontinuation.

These criteria categorize the visit response into the following response classifications:

- *CR with incomplete recovery of neutrophils and platelets (CRi):*

Achievement of CRi requires patients to satisfy all of the following:

- A disappearance of blasts in the peripheral blood.
- A decrease in BM blasts to <5% total BM nucleated cells demonstrated in BM aspirate.
- Absence of Auer rods
- No persistent extramedullary leukaemia

- *Complete Remission:*

Patient satisfies all of the criteria above and in addition has:

- Recovery of Neutrophils to $\geq 1.0 \times 10^9/L$ and Platelets to $\geq 100 \times 10^9/L$
- Transfusion-independence

- *Partial Remission:*

A PR is defined as recovery of neutrophils to $\geq 1.0 \times 10^9/L$ and Platelets to $\geq 100 \times 10^9/L$ and either:

- If the pre-treatment bone marrow blast percentage was 50% to 100%, the percentage of blast must decrease to a value between 5% and 25%
- If the pre-treatment BM blast percentage was 20% to less than 49%, they must decrease by at least half to a value of more than 5%

- A reduction in BM blast cells to <5% but with persistence of Auer rods.

- *Treatment failure:*

Failure to meet the criteria for CR, CRi or PR after 4 cycles of treatment will result in a best response of treatment failure.

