3.1.2 Relapse-Free Survival

Relapse-free survival (RFS) is a secondary endpoint in Parts 1 and 2 and is defined for the sub-group of patients classified as responders for OCRR.

RFS is defined as the time the criteria for remission (CR or CRi) are first met until there is evidence of patient relapse, regardless of whether the patient is still taking study drug or has started other anti-AML treatment prior to relapse. (Note, the onset of the CR/CRi must have been before the start of subsequent anti-AML treatment to be classified as a responder for OCRR). Relapse is defined as:

- The reappearance of leukemic blasts in the peripheral blood or >5% blasts in the bone marrow not attributable to any other cause
- The appearance of new dysplastic changes
- The reappearance of or development of cytologically proven extramedullary disease
- The reappearance of a cytogenetic or molecular abnormality
- Death by any cause

In the event that the blood and bone marrow response assessments for a visit are performed on different dates, RFS will be calculated using the earliest date at which a relapse was detected. For example, if both the peripheral blood and bone marrow were assessed and both found to be indicative of relapse, RFS will use the earlier of the two assessment dates. However, if both were assessed, but only the marrow was found to be indicative of relapse, the date of the marrow assessment would be used as the date of relapse.

As described above, patients who die without evidence of relapse will be considered to have relapsed at the date of death, provided that the death does not occur following two or more missed assessments (up to 56 days following previous assessment). If the death occurs more than 56 days following the previous response assessment, the patient will be censored for RFS at the date of the last efficacy assessment in which they were alive and relapse-free.

Similarly, patients who are determined to have met the criteria for relapse more than 56 days after the last efficacy assessment will also be censored for RFS at the date of the last efficacy assessment in which they relapse-free.

For the purpose of evaluating whether RFS should be censored due to missed visits, a patient will be considered to have missed two assessments if neither the peripheral blood or bone marrow have been assessed for >56 days.

In all study parts, the primary analysis of RFS will be assessed based on the EFR set with a sensitivity analysis based on the FAS.

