4.3 Evaluable for Response Set

The EFR set is defined as a subset of the FAS, excluding any patients with major protocol deviations. Deviations that would end to exclusion from the FAS are:

- Patient does not have AML as defined by the 2016 revision to the WHO classification of myeloid neoplasms and acute leukemia (failure of inclusion criteria 3)
- Patient is eligible for induction therapy (failure of inclusion criteria 5)
- Patients who are diagnosed with *de novo* myeloid sarcoma without bone marrow involvement (satisfying exclusion criteria 1)
- Patients who are diagnosed with acute promyelocytic leukemia with the *PML-RARA* (satisfying exclusion criteria 2)
- Patients who received any other standard or investigational treatment for their leukemia within the last 7 days before starting the first dose of study drug, with the exception of leukapheresis and hydroxyurea (satisfying exclusion criteria 3)

The EFR set will be the primary analysis set used for the evaluation of all efficacy objectives.

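### No baseline marrow blast floor at entry or in the EFR set: patients above 10% and below 20% cannot reach PR by halving, and CRi can be scored from a baseline below 5%

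*Protocol*

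**What the plan says.** **Entry.** Protocol 4.1 criterion 3 requires "Patients who are diagnosed with AML according to the 2016 revision to the World Health Organization classification of myeloid neoplasms and acute leukemia". Criterion 5 admits "Patients who relapsed from prior remission" and patients in whom prior therapy failed. Neither criterion, nor Appendix 1, states a blast percentage. The one exclusion in Protocol 4.2 that turns on marrow involvement is de novo "myeloid sarcoma without bone marrow involvement".

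**Analysis set.** SAP 4.3: "The EFR set is defined as a subset of the FAS, excluding any patients with major protocol deviations". The exclusions listed there, in SAP 5.1 and in Protocol 8.3.3 include nothing on baseline blasts.

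**PR (Protocol 6.2, SAP 3.1.1).** Neutrophils and platelets must recover, and one of three branches must be met:
- The first opens "If the pre-treatment bone marrow blast percentage was 50% to 100"% and asks for a fall to 5-25%.
- The second reads "If the pre-treatment BM blast percentage was 20% to less than 49%, they must decrease by at least half", and the result must stay above 5%.
- The third is a fall below 5% with Auer rods persisting. It has no baseline condition.

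A patient without CR, CRi or PR after 4 cycles is a treatment failure.

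**CRi (same sections).** The marrow condition is "A decrease in BM blasts to <5% total BM nucleated cells demonstrated in BM aspirate". Blood blasts must have disappeared, and there must be no Auer rods and no persistent extramedullary leukaemia. No baseline value is required.

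**Relapse.** The only definition printed is the one for RFS. It includes "The reappearance of leukemic blasts in the peripheral blood or >5% blasts in the bone marrow not attributable to any other cause", and also new dysplasia, extramedullary disease, or a returning cytogenetic or molecular abnormality, none of which carries a marrow blast threshold.

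**The concern.** The response rules are written for patients with substantial marrow disease at baseline, but the entry criteria do not ensure it. Two consequences follow.

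First, a relapsed or refractory patient whose baseline lies below the second PR band can have a proportional fall as large as one that earns PR at 20%, recover counts, and still be labelled a treatment failure. That understates CBR, a secondary endpoint, and removes the patient from time to response.

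Second, a patient who enters with marrow blasts already below 5% and no other visible disease needs only a small fall to meet CRi. That adds a responder to OCRR, which is co-primary in Part 1 and primary in Part 2, on weak evidence of drug effect.

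The stakes are greatest in Part 1. Cohorts have six patients, and the expansion dose is chosen from a cohort showing clinical benefit with tolerable safety (Protocol 3.1, 3.2).

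**Working it through.** The plan states no power, response threshold or expected rate, so there is no figure of its own to reproduce.

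**Step 1: apply the printed rules.** Assume recovered counts, transfusion independence, no blood blasts and no extramedullary disease.

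| Marrow blasts, baseline to on-treatment | Proportional fall | No Auer rods | Auer rods persist |
|---|---|---|---|
| 20% to 10% | (20-10)/20 = 50% | PR | PR |
| 18% to 8% | (18-8)/18 = 56% | failure after 4 cycles | failure after 4 cycles |
| 10% to 5% | (10-5)/10 = 50% | failure after 4 cycles | failure after 4 cycles |
| 19% to 4% | (19-4)/19 = 79% | CR/CRi | PR |
| 4% to 2% | (4-2)/4 = 50% | CR/CRi | PR |
| 4% to 4% | 0% | not CR/CRi if a decrease is enforced; CR/CRi if the program tests only for <5% | failure after 4 cycles |

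**Step 2: find the band that loses PR.** Write b for the baseline. The second branch asks for a value of at most b/2 that is still above 5%. Both can hold only if b/2 > 5, that is, b > 10. The 20% floor therefore closes PR by halving for baselines above 10% and below 20%. At 10% or less, the above-5% condition would close it even without the floor.

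**Step 3: size the effect on CBR.** One missed PR is 1/20 = 5 points in Part 2 and 1/6 = 16.7 points in a Part 1 cohort. The expected loss is r × p, where r is the share of patients in the band and p is the share of those who would halve, stay above 5% and recover counts. Neither is in the documents. Assuming 10-30% for each, the loss runs from 0.1 × 0.1 = 1 point to 0.3 × 0.3 = 9 points.

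**Step 4: size the effect on OCRR.** The planned interval is the two-sided 80% Clopper-Pearson (Protocol 8.4.1, SAP 7.1). For x responders of n, the lower limit is the 0.10 quantile of Beta(x, n-x+1) and the upper limit is the 0.90 quantile of Beta(x+1, n-x).
- 2/20 = 10%: 2.7% to 24.5%.
- 3/20 = 15%, after one entrant below 5% counts as a responder: 5.6% to 30.4%.
- In a six-patient cohort, 0/6 becomes 1/6, a shift of 16.7 points.

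**Step 5: how often this might occur.** Let q be the assumed share of patients who enter below 5% and then meet every CRi condition. The chance of at least one among 20 is 1-(1-q)^20. If the other patients respond at 10%, the expected OCRR is 0.10(1-q)+q.

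| Assumed q | Expected number of 20 | Chance of at least one | Expected OCRR |
|---|---|---|---|
| 5% | 1 | 0.64 | 14.5% |
| 10% | 2 | 0.88 | 19% |
| 20% | 4 | 0.99 | 28% |

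These rows show sensitivity to q. They are not a forecast.

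**The case against.** Several points on the other side stand, and they rule out stronger readings that a reader might infer.

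- **That every patient at 5-19% has no blast-reduction route to PR.** Not so. The Auer-rod branch has no baseline floor, and a fall below 5% can give CR or CRi. What is closed is PR by halving, and the 20% floor is the cause only above 10%. This half never touches OCRR.
- **That any entrant below 5% is scored CRi at Cycle 2 Day 1 with no drug effect.** The printed criterion asks for a *decrease*, so an unchanged 4% does not qualify as written. It would count only if the program ignored that word. Blood blasts and extramedullary disease must also be absent, so the exposure is mainly relapse recognised by cytogenetic, molecular or dysplastic findings.
- **That the plan itself defines relapse at entry as more than 5% blasts.** That definition is written for RFS, and criterion 5 does not refer to it. Applying it at entry is an inference. Whether the WHO classification cited in criterion 3 carries its own blast minimum cannot be settled from these documents.

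It is also fair to say that the study is descriptive with no response threshold to cross, that the PR bands are presented as the adopted IWG criteria, and that the SAP lists marrow results and the investigator's own IWG assessment by patient, so an implausible CRi would be visible. Visibility in a listing does not change the summary tables, however. OCRR is derived by program (SAP 3.1.1), and nothing in the plan tells the programmer how to treat a low baseline. The plan also already keeps one group without marrow disease out of the EFR set (de novo myeloid sarcoma), so the principle is not foreign to it.

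**Conclusion.** The point holds in two limited parts.

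1. The printed PR rules classify an eligible patient with a baseline above 10% and below 20% as a treatment failure after 4 cycles for a response that is PR at 20%, unless the patient reaches CR/CRi or the Auer-rod branch. CBR is understated by 5 points per such patient in Part 2, and time to response loses that patient. This follows from the text and needs no assumption beyond such patients being enrolled, which the entry criteria do not prevent.
2. CRi has no baseline floor, so an entrant below 5% with no blood blasts, Auer rods or extramedullary disease can become an OCRR responder on a fall such as 4% to 2%. Each one adds 5 points in Part 2 or 16.7 points in a six-patient cohort.

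The number of patients of either kind is not given, so the total effect is unknown. The documents do not support a claim that OCRR will be materially inflated, only that nothing in the plan prevents it. The change is worth making because it is cheap and the cohorts are small.

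**What to change.** **(a) EFR set.** In SAP 4.3 and 5.1 and Protocol 8.3.3, exclude from the EFR set only patients with baseline marrow blasts below 5% *and* no blood blasts or extramedullary disease. A plain 5% marrow floor would also drop patients with measurable disease elsewhere. Keep the excluded patients in the FAS and report the FAS result in both parts. SAP 3.1.1 promises that sensitivity analysis for all parts, whereas SAP 4.2 and Table 1 confine it to Part 2, so these need to agree. In the Part 2 example above, the EFR result would be 2/19 = 10.5% beside an FAS result of 3/20 = 15%.

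**(b) PR for analysis.** For CBR and time to response, apply the second branch's test (at least halved, still above 5%) to baselines below 20% as well. State that this opens PR only for baselines above 10% and departs slightly from the printed bands.

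**Reconciliation.** PR also feeds the treatment-failure and discontinuation text in Protocol 3.4 and 4.3. The sponsor must reconcile those passages with any analysis definition. No discontinuation rule is proposed here.

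**Cost.** Wording in both documents and a small programming change, which should state that *decrease* in the CRi rule is enforced. A patient or two may leave the EFR set, and strict comparability with the printed PR bands is slightly reduced. Reporting CBR under both PR definitions would show the effect of that departure.

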4.2 Exclusion Criteria

Patients will not be enrolled in the study if they meet any of the following criteria:

1. Patients who are diagnosed with *de novo* myeloid sarcoma without bone marrow involvement

2. Patients who are diagnosed with acute promyelocytic leukemia/retinoic acid receptor alpha (*PML-RARA*)
3. Patients who received any other standard or investigational treatment for their leukemia within the last 7 days before starting the first dose of study drug, with the exception of leukapheresis and hydroxyurea
4. Patients with unresolved serious toxicity (\geq CTCAE 4.03 Grade 2) from prior administration of standard or investigational treatment for their leukemia
5. Patients who have a positive test for human immunodeficiency virus (HIV), viral hepatitis C infection (patients with sustained viral response are not excluded), active viral hepatitis B infection (positive hepatitis B surface antigen [HBsAg]) with hepatitis B virus DNA exceeding 2000 IU/ml
6. Patients who have a known history of liver cirrhosis Child-Pugh score B or C
7. Patients who have any history of other malignancy unless in remission for more than 1 year (skin carcinoma and carcinoma-in-situ of uterine cervix treated with curative intent is not exclusionary)
8. Female patients who are pregnant or breast-feeding
9. Patients with a known history of alcohol or drug addiction on the basis that there could be a higher risk of non-compliance to study treatment per Investigator's discretion
10. Patients with a history or presence of a clinically significant condition which in the opinion of the Investigator could jeopardize the safety of the patient or the validity of the study results
11. Patients who have been previously treated with ASLAN003

